9.5.1.6.6 ELECTROCARDIOGRAMS

Electrocardiograms will be obtained as designated in the Schedule of Procedures/Assessments ([Table 8](#)). Complete, standardized, 12-lead ECG recordings that permit all 12 leads to be displayed on a single page with an accompanying lead II rhythm strip below the customary 3×4 lead format are to be used. In addition to a rhythm strip, a minimum of 3 full complexes should be recorded from each lead simultaneously. Subjects must be in the recumbent position for a period of 5 minutes prior to the ECG. Electrocardiograms obtained at C1D1 and C1D8 should be performed just prior to and immediately after receiving the eribulin mesylate infusion.

An ECG abnormality may meet the criteria of an AE as described in this protocol (see [Section 9.5.1.6](#)) and the CRF Completion Guidelines. In these instances, the AE corresponding to the ECG abnormality will be recorded on the Adverse Events CRF.

9.5.1.6.7 OTHER SAFETY ASSESSMENTS

Eastern Cooperative Oncology Group Performance Status

Eastern Cooperative Oncology Group performance status will be assessed at the Screening Visit, Day 1 of each treatment cycle, and at End of Treatment Visits. The table in [Appendix 7](#) will be used to assess performance status.

9.5.2 Schedule of Procedures/Assessments

Refer to [Table 8](#) for the description and timing of each procedure and assessment in the Pretreatment, Treatment, and Posttreatment Phases.

9.5.2.1 Schedule of Procedures/Assessments

Table 8 presents the schedule of procedures and assessments for the study.

Table 8 Schedule of Procedures/Assessments

Phase	Pretreatment	Treatment		Posttreatment	
Period	Screening	Treatment Cycle 1 Through Last Cycle (21-day cycle)		End of Treatment	Follow-up ^o
Day	Days -21 to -1	Day 1 (includes Baseline C1/D1)	Day 8	Within 30 ^a days of final treatment	Every 12 weeks
Assessments					
Informed consent	X				
Inclusion and Exclusion Criteria	X				
Demographic ^b	X				
Medical/surgical history	X				
TNM Staging ^c	X				
mTNBC diagnosis	X				
Prior anticancer therapy	X				
Pregnancy test ^d	X				
PK ^e		X	X		
Tumor tissue for PD-L1 expression	X				
ECG ^f	X	X ^f	X ^f		
Hematology ^g	X	X	X	X	
Chemistry ^h	X	X		X	
TSH and free T4 levels ⁱ	X	X		X	
Urinalysis (dipstick) ^j	X	X		X	
ECOG	X	X		X	
Vital signs	X	X	X	X	
Physical examination ^k	X	X	X	X	
Eribulin mesylate ^l		X	X		
Pembrolizumab ^m		X			
Disposition				X	

Table 8 Schedule of Procedures/Assessments

Phase	Pretreatment	Treatment		Posttreatment	
Period	Screening	Treatment Cycle 1 Through Last Cycle (21-day cycle)		End of Treatment	Follow-up ^o
Day	Days -21 to -1	Day 1 (includes Baseline C1/D1)	Day 8	Within 30 ^a days of final treatment	Every 12 weeks
Tumor assessments ⁿ		Throughout Study			X
Adverse events/SAEs		Throughout Study			X
Concomitant medications		Throughout Study			
Survival information ^o				X	

AE = adverse event, β -hCG = beta-human chorionic gonadotropin, C1D1 = Cycle 1 Day 1, CT = computerized tomography, eCRF = electronic case report form, ECG = electrocardiogram, ECOG = Eastern Cooperative Oncology Group, CR = complete response, irCR = immune-related Complete Response, IV = intravenous, PK = pharmacokinetic, SAE = serious adverse event, MRI = magnetic resonance imaging, RBC = red blood cells, TNM = tumor-node-metastases, TSH = thyroid stimulating hormone, T4 = thyroxine, WBC = white blood cell.

- a: End of Treatment assessments for all subjects will be collected within 30 days of the last dose of study drug. Subjects with SAEs and/or ECIs at the time of End of Treatment will be followed for 90 days after the last dose of study drug or, if the subject initiates new anticancer therapy, for 30 days following the last dose of study drug, whichever is earlier. However, treatment-emergent peripheral neuropathy of any grade will be followed until resolution or until another anticancer therapy is started, whichever occurs first. All SAEs should be followed to resolution or, if resolution is unlikely, to stabilization.
- b: Demography information includes date of birth (or age), sex, and race/ethnicity.
- c: TNM staging at the time of diagnosis should be recorded in the eCRF.
- d: A serum (6-mL blood sample will be collected) or urine β -hCG test will be performed at the Screening Visit for premenopausal women and postmenopausal women who have been amenorrheic for less than 12 months. If a negative screening pregnancy test is obtained more than 72 hours before the planned first dose of pembrolizumab and eribulin mesylate, a separate serum or urine sample must be obtained and tested at the Baseline Visit assessment on C1D1.
- e: Pharmacokinetic blood samples will be collected only for eribulin mesylate PK analysis. Time points for PK sample collections are as follows: For all Phase 1b subjects, PK samples will be collected on C1D1 at predose (0 hour), 15, 30 minutes and 1, 2, 4, 8, 24, 48, 72, 96, 120, and 144 hours after the study drug infusion. For Phase 2 subjects, PK samples will be collected, if feasible, on C1D1 (at the end of the infusion, 0.5 to 6 hours and 24 to 120 hours after study drug infusion) and on C1D8 (predose and at the end of the infusion).
- f: Electrocardiogram (ECG) will be performed at Screening, C1D1, C1D8, and at any unscheduled visits as clinically indicated. ECGs obtained at C1D1 and C1D8 should be performed just prior to and immediately after receiving the eribulin mesylate infusion.

- g: Hematology laboratory assessment must be reviewed prior to every eribulin mesylate administration. Cycle 1 Day 1 hematology assessments may be performed within 3 days prior to the scheduled visit. Subsequent hematology assessments may be performed within 24 hours before the scheduled visit.
- h: Chemistry laboratory assessment must be reviewed prior to every pembrolizumab administration. Cycle 1 Day 1 chemistry assessments may be performed within 3 days prior to the scheduled visit. Subsequent chemistry assessments may be performed within 24 hours before the scheduled visit.
- i: Assessment of TSH and free T4 levels are to be performed at the Screening Visit and then every 2 cycles (starting at Cycle 2) throughout the study. As of Protocol Amendment 05, TSH and T4 will be done at the discretion of the investigator.
- j: Urinalysis will be assessed at the Screening Visit and on Day 1 at Cycles 2 and 4. Urinalysis will include glucose, ketones, pH, protein, WBCs, hemoglobin (or RBCs), and specific gravity. If urinalysis suggests a urinary tract infection, or if clinically indicated, a urine microscopy, culture, and sensitivity should be performed at the institution's laboratory.
- k: Symptom-directed physical examination and abnormal clinically significant findings should be recorded on AE page of the CRF.
- l: Eribulin mesylate will be given immediately following pembrolizumab on Day 1 (± 3 day window is allowed) and alone on Day 8 (± 2 day window is allowed) of a 3 week cycle.
- m: Pembrolizumab will be given prior to eribulin mesylate, only on Day 1 of a 3-week cycle (± 3 day window is allowed).
- n: Screening tumor assessments using CT of the chest, abdomen, and pelvis and other areas of known disease or newly suspected disease should be performed within 28 days prior to C1D1. Scans of the abdomen, pelvis, and other areas of the body may be done with MRI instead of CT, but evaluation of the chest should be done with CT. CT scans should be performed with oral and iodinated IV contrast and MRI scans with IV gadolinium chelate unless there is a medical contraindication to contrast. If iodinated IV contrast is contraindicated, chest CT should be done without IV contrast.

Treatment Phase: Tumor assessments of the chest, abdomen, and pelvis and other areas where scans were performed at screening or newly suspected disease should be performed every 9 weeks ± 1 week after the start of study treatment (or sooner if there is evidence of progressive disease) and should use the same methodology (CT or MRI) and scan acquisition techniques (including use or nonuse of IV contrast) as were used for the screening assessments. Objective responses must be confirmed at least 4 weeks later (eg, generally at the next tumor assessment time point).

Screening brain scans will be performed by MRI pre- and post- gadolinium or CT with contrast within 28 days prior to C1D1. During the Treatment Phase, CT/MRI of the brain will be performed if clinically indicated, and within a target of 1 week after a subject achieves an irCR. For subjects with history of treated brain metastases, brain scans will be performed at tumor assessment time points if clinically indicated. The same methodology and scan acquisition techniques used at screening should be used throughout the study to ensure comparability.

A bone scan (99m -technetium polyphosphonate scintigraphy, whole body bone MRI, or 18 F-NaF) to assess bone metastases will be performed within 6 weeks prior to C1D1 (historical scans are acceptable) and then every 27 weeks (within that 27th week) from C1D1, or sooner if clinically indicated. In subjects whose body CT/MRI scans indicate CR has been achieved, a bone scan will be required at confirmation of CR to exclude new bone metastases. The same methodology and acquisition techniques used at screening should be used throughout the study to ensure comparability. Lesions detected on bone scans must be followed with cross-sectional imaging.

In subjects who discontinue study therapy without documented disease progression, every effort should be made to continue monitoring their disease status by radiologic imaging every 9 weeks \pm 1 week during Year 1, and every 9 to 12 weeks \pm 1 week thereafter per standard of care, until (1) the start of new anticancer treatment, (2) disease progression (3) death, or (4) the end of the study, whichever occurs first.

- o: As of Protocol Amendment 05, Follow-Up assessments in the Posttreatment Phase will not be performed after the subject completes the Off-Treatment visit assessments (or after the 90 day monitoring for subjects with SAEs and/or events of clinical interest).

9.5.2.2 Description of Procedures/Assessments Schedule

Refer to [Table 8](#) for the Schedule of Procedures/ Assessments.

9.5.3 Appropriateness of Measurements

All clinical assessments are standard measurements commonly used in oncology studies. The safety assessments to be performed in this study, including hematology analyses, blood chemistry tests, pregnancy tests, radiologic studies, and assessment of AEs, are standard ICH GCP evaluations to ensure subject safety. The use of RECIST v1.1 for tumor assessment is widely accepted. See [Appendix 3](#).

9.5.4 Reporting of Serious Adverse Events, Pregnancy, and Events Associated with Special Situations

9.5.4.1 Reporting of Serious Adverse Events

All SERIOUS ADVERSE EVENTS, regardless of their relationship to study treatment, must be reported on a completed SAE form by email or fax as soon as possible but no later than 24 hours from the date the investigator becomes aware of the event.

Serious adverse events and ECIs, regardless of causality assessment, must be collected through the last visit and for 90 days after the subject's last dose, or 30 days following the last doses if the subject initiates new anticancer therapy, whichever is earlier. All SAEs and/or ECIs must be followed to resolution or, if resolution is unlikely, until the event or sequelae stabilize. Any SAE judged by the investigator to be related to the study treatment or any protocol-required procedure should be reported to the sponsor regardless of the length of time that has passed since study completion.

The detailed contact information for reporting of SAEs is provided in the Investigator Study File.

For urgent safety issues, please ensure that all appropriate medical care is administered to the subject and contact the appropriate study team member listed in the Investigator Study File.

It is very important that the SAE report form be filled out as completely as possible at the time of the initial report. This includes the investigator's assessment of causality.

Any follow-up information received on SAEs should be forwarded within 24 hours of its receipt. If the follow-up information changes the investigator's assessment of causality, this should also be noted on the follow-up SAE form.

Preliminary SAE reports should be followed as soon as possible by detailed descriptions including copies of hospital case reports, autopsy reports, and other documents requested by the sponsor.

The investigator must notify his/her IRB/IEC of the occurrence of the SAE in writing, if required by his/her institution. A copy of this communication must be forwarded to the sponsor to be filed in the sponsor's Study Master File.

9.5.4.2 Reporting of Pregnancy and Exposure to Study Drug Through Breastfeeding

Any pregnancy in which the estimated date of conception is either before the last visit or within 120 days of last study treatment or 30 days following last study treatment if the subject initiates new anticancer therapy, whichever is earlier, must be reported. Also, any exposure to study drug through breastfeeding during study treatment or within 120 days of last study treatment or 30 days following last study treatment if the subject initiates new anticancer therapy, whichever is earlier, must be reported.

If an adverse outcome of a pregnancy is suspected to be related to study drug exposure, this should be reported regardless of the length of time that has passed since the exposure to study treatment.

A congenital anomaly, death during perinatal period, an induced abortion, or a spontaneous abortion are considered to be an SAE and should be reported in the same time frame and in the same format as all other SAEs (see Reporting of Serious Adverse Events, [Section 9.5.4.1](#)).

Pregnancies or exposure to study drug through breastfeeding must be reported by fax or email as soon as possible but no later than 1 business day from the date the investigator becomes aware of the pregnancy. The contact information for the reporting of pregnancies and exposure to study drug through breastfeeding is provided in the Investigator Study File. The Pregnancy Report Form must be used for reporting. All pregnancies must be followed to outcome. The outcome of the pregnancy must be reported as soon as possible but no later than 1 business day from the date the investigator becomes aware of the outcome.

A subject who becomes pregnant must be withdrawn from the study (all off-treatment study assessments should apply).

9.5.4.3 Reporting of Events Associated with Special Situations

9.5.4.3.1 REPORTING OF ADVERSE EVENTS ASSOCIATED WITH STUDY DRUG OVERDOSE, MISUSE, ABUSE, OR MEDICATION ERROR

Study drugs will be given IV by the study staff at the investigator site. No abuse or errors are anticipated.

Adverse events associated with study drug overdose, misuse, abuse, and medication error refer to AEs associated with uses of the study drugs outside of that specified by the protocol. Overdose, misuse, abuse, and medication error are defined as follows:

Overdose	Accidental or intentional use of the study drug in an amount higher than the protocol-defined dose. For this study, an overdose of pembrolizumab will be defined as ≥ 1000 mg (5 times the 200 mg dose). No specific information is available on the treatment of overdose of pembrolizumab. In the event of overdose, the subject should be observed closely for signs of toxicity. Appropriate supportive treatment should be provided if clinically indicated.
Misuse	Intentional and inappropriate use of study drug not in accordance with the protocol.
Abuse	Sporadic or persistent intentional excessive use of study drug accompanied by harmful physical or psychological effects
Medication error	Any unintentional event that causes or leads to inappropriate study drug use or subject harm while the study drug is in the control of the healthcare professional, subject, or consumer. Such events may be related to professional practice, healthcare products, occupational exposure, procedures, or systems, including prescribing, order communication, product labeling/packaging/nomenclature, compounding, dispensing, distribution, administration, education, monitoring, or use.

All AEs associated with overdose, misuse, abuse, or medication error should be captured on the Adverse Event CRF and also reported using the procedures detailed in Reporting of Serious Adverse Events ([Section 9.5.4.1](#)), even if the AEs do not meet serious criteria.

Abuse is always to be captured as an AE. If the AE associated with an overdose or medication error does not meet serious criteria, it must still be reported using the SAE form and in an expedited manner but should be noted as nonserious on the SAE form and the Adverse Event CRF.

9.5.4.3.2 REPORTING OF STUDY-SPECIFIC EVENTS/EVENTS OF CLINICAL INTEREST

Study-specific events (Events of Clinical Interest [ECIs]) should always be considered as serious important medical events and be entered on the Adverse Event CRF and reported using the procedures detailed in Reporting of Serious Adverse Events ([Section 9.5.4.1](#)), even if the study-specific event does not meet other serious criteria.

Events of clinical interest for this study include: an elevated AST or ALT lab value that is greater than or equal to $3 \times$ ULN and an elevated total bilirubin lab value that is greater than or equal to $2 \times$ ULN and, at the same time, an alkaline phosphatase lab value that is less than $2 \times$ ULN, as determined by way of protocol-specified laboratory testing or unscheduled laboratory testing.*

*Note: These criteria are based upon available regulatory guidance documents. The purpose of the criteria is to specify a threshold of abnormal hepatic tests that may require an

additional evaluation for an underlying etiology. The study site guidance for assessment and follow up of these criteria can be found in the Investigator Study File Binder (or equivalent).

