9.3.1 Inclusion Criteria

Subjects must meet all of the following criteria to be included in the study.

1. Females or males, aged ≥ 18 years at the time of signing the informed consent form (ICF)
2. Metastatic triple-negative breast cancer (confirmed from most recent tissue sample) meeting the following criteria:
 - a. Estrogen receptor (ER) and progesterone receptor negative (a tumor is ER and/or progesterone receptor positive if at least 1% of the cells examined have estrogen and/or progesterone receptors) and human epidermal growth factor receptor 2 (HER2) -negative (defined as immunohistochemistry (IHC) $<2+$ or fluorescence in situ hybridization (FISH) negative).
 - b. Previously treated with 0 to 2 lines of systemic anticancer therapy (cytotoxic or targeted anticancer agents) in the metastatic setting. Hormonal therapy and bone metastases treatment (eg, bisphosphonates, denosumab, etc) are not considered forms of systemic anticancer therapy.
3. Presence of measurable disease meeting the following criteria:
 - a. At least 1 lesion of ≥ 10 mm in long axis diameter for nonlymph nodes or ≥ 15 mm in short axis diameter for lymph nodes that is serially measurable according to RECIST 1.1 using either computerized tomography or magnetic resonance imaging or panoramic and close-up color photography.
 - b. Lesions that have had radiotherapy must show subsequent radiographic evidence of increased size to be deemed a target lesion.
4. Life expectancy of ≥ 3 months
5. Eastern Cooperative Oncology Group (ECOG) performance status (PS) of 0 or 1
6. Adequate renal function as evidenced by serum creatinine ≤ 1.5 mg/dL or calculated creatinine clearance ≥ 50 mL/minute according to the Cockcroft and Gault formula
7. Adequate bone marrow function, defined as:
 - a. Absolute neutrophil count (ANC) $\geq 1.5 \times 10^9/L$
 - b. Hemoglobin (Hb) ≥ 10.0 g/dL (can be corrected by growth factor or transfusion)
 - c. Platelet count $\geq 100 \times 10^9/L$
8. Adequate liver function, defined as:
 - a. Total bilirubin $\leq 1.5 \times$ upper limit of normal (ULN)

- b. Alkaline phosphatase (ALP), alanine aminotransferase (ALT), and aspartate aminotransferase (AST) $\leq 3 \times$ ULN unless there are bone metastases, in which case liver specific alkaline phosphatase must be separated from the total and used to assess the liver function instead of the total alkaline phosphatase. ALT and AST $\leq 5 \times$ ULN if subject has liver metastases

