9.5.1.6.3 LABORATORY MEASUREMENTS

Clinical laboratory tests to be performed, including hematology, chemistry, and urinalysis, are summarized in [Table 7](#). Subjects should be in a seated or supine position during blood collection. The Schedule of Procedures/Assessments ([Table 8](#)) shows the visits and time points at which blood for clinical laboratory tests and urine for urinalysis will be collected in the study.

Efforts should be made to conduct study visits on the day scheduled. However, the Cycle 1 Day 1 hematology and chemistry assessments may be performed within 3 days prior to the scheduled visit, while subsequent hematology or chemistry assessments may be performed within 24 hours prior to the scheduled visit. On all occasions when study drug administration is scheduled, all hematology, blood chemistry, and urinalysis samples are to be obtained prior to study drug administration and results reviewed prior to administration/dispensing of study drug. Refer to [Appendix 2](#) for the management of clinically significant laboratory abnormalities.

Table 7 Clinical Laboratory Tests

Category	Parameters
Hematology	Hematocrit, hemoglobin, platelets, RBC count, and WBC count with differential (bands, basophils, eosinophils, lymphocytes, monocytes, neutrophils), ANC
Clinical Chemistry	
Electrolytes	Sodium, potassium, chloride, calcium, magnesium
Liver Function Tests	ALT, AST, alkaline phosphatase, total bilirubin, direct bilirubin
Renal Function	BUN, serum creatinine
Thyroid Function	TSH, T4 ^a
Pregnancy	Serum β-hCG (if urine not done)
Other	LDH, total protein, glucose (fasting ^b)
Urinalysis	Glucose, ketones, pH, protein, RBCs, WBCs, specific gravity Urine β-hCG (if serum not done)

ALT = alanine aminotransferase, ANC = absolute neutrophil count, AST = aspartate aminotransferase, β-hCG = beta-human chorionic gonadotropin, BUN = blood urea nitrogen, LDH = lactate dehydrogenase, RBC = red blood cells, T4 = thyroxine, TSH = thyroid stimulating hormone, WBC = white blood cells.

a: Thyroid function will be assessed at the Screening Visit and then every 2 cycles (starting at C2) throughout the study. As of Protocol Amendment 05, TSH and T4 will be done at the discretion of the investigator.

b: Fasting glucose at Screen only.

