6.6.3 Adverse Events

All Adverse Events (AE) will be graded by the investigators using CTCAE v4.03. The AE verbatim descriptions (investigator terms from the CRF) will be classified into standardized medical

terminology using the Medical Dictionary for Regulatory Activities (MedDRA). Adverse events will be coded to the MedDRA (Version 22.0) lower level term (LLT) closest to the verbatim term. The linked MedDRA preferred term (PT) and primary system organ class (SOC) are also captured in the database.

The incidence of TEAEs will be summarized descriptively. A TEAE is defined as an AE that emerged during treatment or up to 30 days (90 days for SAEs and /or events of clinical interest) following last dose of study drug, having been absent at pretreatment (Baseline) or

- Reemerged during treatment or up to 30 days (90 days for SAEs and /or events of clinical interest) following last dose of study drug, having been present at pretreatment (Baseline) but stopped before treatment, or
- Worsened in severity during treatment or up to 30 days (90 days for SAEs and /or events of clinical interest) following last dose of study drug relative to the pretreatment state, when the AE was continuing.

Per protocol amendment 1, Events of clinical interest (ECI) for this trial include: an elevated aspartate aminotransferase (AST) or alanine aminotransferase (ALT) lab value that is greater than or equal to $3 \times$ ULN and an elevated total bilirubin lab value that is greater than or equal to $2 \times$ ULN and, at the same time, an alkaline phosphatase lab value that is less than $2 \times$ ULN, as determined by way of protocol-specified laboratory testing or unscheduled laboratory testing.

We used the following AE PT terms to identify ECI above:

- ALT increased
- AST increased
- Blood bilirubin increased
- Blood alkaline phosphatase increased

Only those AEs that are treatment emergent will be included in summary tables. All AEs, treatment emergent or otherwise, will be presented in subject data listings.

An overview table, including the incidence of and the number of subjects with TEAEs, TEAEs with grade 3 or above, serious adverse events (SAEs), deaths, and TEAEs that led to death, treatment discontinuation, dose reduction, or dose interruption will be provided.

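### The hepatic event of clinical interest does not say which alkaline phosphatase counts in bone metastases, and no specified SAP table shows the joint liver signal

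*Protocol*

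**What the plan says.** Protocol 9.5.4.3.2 sets three laboratory conditions that must hold together:

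- "an elevated AST or ALT lab value that is greater than or equal to" 3×ULN;
- "an elevated total bilirubin lab value that is greater than or equal to" 2×ULN;
- "and, at the same time, an alkaline phosphatase lab value that is less than" 2×ULN.

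The ALP in the third condition is unqualified, and bone metastases are not mentioned. The stated purpose is to "specify a threshold of abnormal hepatic tests that may require an" additional search for a cause. An event that meets the rule is treated as serious whatever its other features, and it follows the 24-hour SAE route of Protocol 9.5.4.1.

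Inclusion criterion 8b (Protocol 9.3.1) caps ALP, ALT and AST at 3×ULN. With bone metastases it adds that "liver specific alkaline phosphatase must be separated from the total and used to assess the liver function instead of the total alkaline phosphatase".

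Table 7 (Protocol 9.5.1.6.3) gives the liver panel as "ALT, AST, alkaline phosphatase, total bilirubin, direct bilirubin". No ALP fraction is listed.

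SAP 6.6.3 repeats the three-part definition, "as determined by way of protocol-specified laboratory testing or unscheduled laboratory testing". It then names four MedDRA preferred terms by which the ECI is identified: raised ALT, raised AST, raised blood bilirubin and raised blood ALP.

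**The concern.** At entry the protocol treats total ALP as the wrong value for judging the liver when bone metastases are present. It then builds a hepatic reporting trigger on an ALP value without carrying that provision over. If sites apply the trigger to the scheduled ALP, a raised value of bone origin switches it off, however high AST, ALT and bilirubin go.

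At stake is the one laboratory rule in the protocol that makes a hepatic finding a serious event without further judgement. The drugs under study include one for which Table 4 gives specific guidance on immune-related liver abnormalities. A reader of the study report would also expect to see how many subjects had the joint AST/ALT and bilirubin signal, and the SAP should supply that number.

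**Working it through.** No sample size, power or event count is involved, so the check is one of logic.

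**1. The rule.** ECI = (AST or ALT ≥3×ULN) and (total bilirubin ≥2×ULN) and (ALP <2×ULN). If the ALP used is ≥2×ULN, the result is negative whatever the other values are.

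**2. Which ALP.** The sections do not agree on one:

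| Place | ALP referred to |
|---|---|
| Protocol 9.3.1, criterion 8b, bone metastases | Liver-specific fraction in place of total |
| Protocol 9.5.1.6.3, Table 7 | ALP, no fraction listed (presumably total; an inference) |
| Protocol 9.5.4.3.2 | ALP, unqualified |
| SAP 6.6.3, definition | ALP, unqualified |
| SAP 6.6.3, identification | A preferred term for raised ALP |

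**3. Can an eligible subject sit in the blocked range?** Yes, by two routes.

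- With bone metastases, the 3×ULN cap applies to the liver-specific fraction. Total ALP has no stated upper limit.
- Without bone metastases, ALP may be up to 3×ULN at entry, so values from 2 to 3×ULN are eligible and already fail the ALP condition.

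**4. Illustration.** Take AST 4×ULN and bilirubin 2.5×ULN on one draw.

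| ALP used | AST/ALT ≥3×ULN | Bilirubin ≥2×ULN | ALP <2×ULN | ECI |
|---|---|---|---|---|
| 1.5×ULN | yes | yes | yes | met |
| 2×ULN or more, even if all from bone | yes | yes | no | not met |

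**5. What the second subject loses.** The finding is not automatically serious and does not automatically go by the SAE route. Protocol 9.5.4.1 and the treatment-emergent window in SAP 6.6.3 also give ECIs 90 days after the last dose, against 30 days for ordinary AEs. Under those sections a masked, otherwise non-serious event on days 31–90 falls outside the window. (Protocol 9.5.1.6.1 gives ECIs 30 days, which is a separate inconsistency.)

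**6. What remains.** The investigator can record an AE, or an SAE on medical judgement (Protocol 9.5.1.6.1 and 9.5.1.6.2). The hepatic row of Table 4 has no ALP condition. Under Appendix 2, bilirubin above 1.5×ULN is at least Grade 2, so bilirubin ≥2×ULN appears in the graded tables of SAP 6.6.5. Those tables take one parameter at a time and show the shift to worst grade. They do not show whether AST/ALT and bilirubin were raised together.

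**7. The SAP count.** Four separate preferred terms replace the three-part rule. The SAP does not say whether one term is enough or how the terms combine. A raised ALP points towards an ECI there, while in the protocol rule it rules one out. No specified table therefore gives the joint signal, with or without the ALP condition.

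**8. Size.** Neither document gives the share of subjects with bone metastases or with ALP ≥2×ULN. Purely as an assumption, if 20–40% of 170 subjects had bone metastases and 10–30% of those had ALP ≥2×ULN, the count would run from 170 × 0.20 × 0.10 = 3.4 to 170 × 0.40 × 0.30 = 20.4. These are subjects in whom the rule would be blocked, not missed events. A missed event also needs the AST/ALT and bilirubin rises, for which the documents offer no rate.

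**The case against.** The strongest reply is that little is lost. Criterion 8b is an eligibility rule and was never said to govern later reporting. The word total does not appear in the ECI text, and unscheduled tests count, so a fractionated ALP is not excluded. The criteria are said to rest on regulatory guidance, and site instructions sit in the Investigator Study File, which is not available here and may cover bone disease. Hepatic abnormality is also covered by Table 4, the Phase 1b DLT definition, AE and SAE judgement, and graded laboratory summaries.

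Most of this stands, and it rules out four stronger readings that a reader might infer:

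- *The event can never be met in bone metastases.* The rule is blocked only while the ALP used is ≥2×ULN, and bone metastases alone do not imply that.
- *Liver injury would go undetected.* The components are still recorded and graded; what is lost is the automatic serious handling.
- *The ECI incidence under the SAP is biased downward.* The SAP counts by preferred term and does not apply the ALP condition, so this does not follow.
- *The protocol says total ALP does not measure the liver.* It gives a substitution rule for entry only.

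The reply does not remove the ambiguity. Criterion 8b gives assessment of liver function as its reason, and that is also the ECI's purpose. Nor does it supply the missing joint count, because Table 4 is management guidance for events judged related to pembrolizumab, not a reporting trigger.

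**Conclusion.** The point holds in a limited form. The ECI definition leaves open which ALP applies in bone metastases, although criterion 8b names the liver-specific fraction there. If sites use the ALP in Table 7, a subject with ALP ≥2×ULN cannot trigger automatic serious-event handling for concurrent AST/ALT and bilirubin rises until ALP falls below that level. The same is true of subjects without bone metastases who enter with ALP of 2–3×ULN.

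This rests on one inference, that the ALP in Table 7 is total ALP. The number of events affected cannot be derived and may be zero. The primary efficacy analyses are not touched.

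The SAP gap is more certain because it needs no assumption about prevalence: SAP 6.6.3 states a joint laboratory rule and then identifies the event by terms that do not implement it, one of which runs the opposite way.

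**What to change.** **SAP 6.6.3 and 6.6.5.** Add a laboratory table giving the number of subjects with concurrent AST or ALT ≥3×ULN and total bilirubin ≥2×ULN, once with and once without ALP <2×ULN. Show it overall, and for subjects with bone metastases or baseline ALP ≥2×ULN. State what counts as concurrent (for example, the same collection date), and include unscheduled draws, since the definition does. State how this table relates to the preferred-term identification.

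**Protocol 9.3.1 (8b), 9.5.1.6.3 (Table 7) and 9.5.4.3.2, with SAP 6.6.3.** Reconcile these on which ALP the ECI refers to when bone metastases are present. Which value to use is a clinical decision for the sponsor.

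**Cost.** The table uses data already collected (the liver panel, baseline metastases and baseline ALP), so it needs no new visit or assay. Reconciling the text is a short edit if the ECI keeps the ALP in Table 7. Any choice that relies on a fraction would need a test that Table 7 does not list. The small downside is that a few more hepatic cases may be flagged, some of them due to disease.
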